4. SELECTION OF STUDY POPULATION

4.1 Inclusion Criteria

In order to participate in this study, all subjects must meet ALL of the inclusion criteria described:

1. Individuals 6 through 47 months of age on the day of informed consent.
2. Individuals whose parent(s)/ LAR(s) have voluntarily given written informed consent after the nature of the study has been explained according to local regulatory requirements, prior to study entry.
3. Individuals who can comply with study procedures, including follow-up¹.
4. Individual who is in generally good health as per the Investigator's medical judgement.

Prior to receipt of second study vaccination, subjects must be re-evaluated to confirm that they are eligible for subsequent vaccination. If subjects do not meet criteria 3 and/or 4 of the original inclusion criteria listed above, they should not receive additional vaccinations.

4.2 Exclusion Criteria

Each subject must not have:

1. Acute (severe) febrile illness (see [Section 4.3 Criteria for Delay of Vaccination](#)).
2. History of any anaphylaxis, serious vaccine reactions or hypersensitivity, including allergic reactions, to any component of vaccine or medical equipment whose use is foreseen in this study.
3. Clinical conditions representing a contraindication to intramuscular vaccination and blood draws. These may include known bleeding disorders, or treatment with anticoagulants in the 3 weeks preceding vaccination.
4. A known history of Guillain-Barre Syndrome or other demyelinating diseases such as encephalomyelitis and transverse myelitis.

¹ A subject and parent(s)/legally acceptable representative(s) are considered to be compliant if the Investigator judges that the subject will complete the Subject Diary Card, return for all the follow-up visits, be available for telephone calls, as scheduled in the study.

5. Abnormal function of the immune system resulting from clinical conditions, which include:
 - a. Known or suspected congenital or acquired immunodeficiency.
 - b. Systemic administration of corticosteroids (PO/IV/IM) at any dose for more than 14 days, within 90 days prior to informed consent. Topical, inhaled and intranasal corticosteroids are permitted. Intermittent use (1 dose in 30 days) of intra-articular corticosteroids is also permitted.
 - c. Administration of antineoplastic and immunomodulating agents or radiotherapy within 90 days prior to informed consent.
6. Received immunoglobulins or any blood products within 180 days prior to informed consent.
7. Received an investigational or non-registered medicinal product within 30 days prior to informed consent, or intend to participate in another clinical trial during the study.
8. Study personnel, family and household members of study personnel should not participate.
9. Any other clinical condition that, in the opinion of the investigator, might interfere with the results of the study or pose additional risk to the subject due to participation in the study.
10. Received influenza vaccination or has had documented influenza disease in the last 6 months prior to informed consent.
11. Received any other vaccines than influenza vaccine within 14 days (for inactivated vaccines) or 28 days (for live vaccines) prior to study vaccination or who are planning to receive any vaccine within 28 days after study vaccination.

Prior to receipt of second study vaccination, subjects must be evaluated to confirm that they are eligible for subsequent vaccination. If subjects meet any of the original exclusion criteria listed above or experienced severe tolerability issues after first study vaccination, they should not receive additional vaccinations. However, these subjects should be encouraged to continue study participation. This review of eligibility should be documented in the source document and the reason for not administering a scheduled study vaccine should be documented in the eCRF.

4.3 Criteria for Delay of Vaccination

There may be instances when individuals meet all eligibility criteria for vaccination yet have a transient clinical circumstance which warrant delay of vaccination (ie, body temperature elevation $\geq 38.0^{\circ}\text{C}$ / $\geq 100.4^{\circ}\text{F}$) within 3 days prior to intended study

vaccination, or use of antipyretics and/or analgesic medications within 24 hours prior to vaccination. Under such circumstances, a subject may be considered eligible for study enrollment after the above defined window for delay has passed and inclusion/exclusion criteria have been rechecked, and if the subject is confirmed to be eligible. In these instances, missing the visit window is not considered a protocol deviation.

5. STUDY PROCEDURES

The sections that follow provide an overview of the procedures that are to be followed in enrolling, evaluating, and following subjects who participate in this clinical study. Visits can be either clinic visits or safety assessment call, as specified in [Table 5-1](#) below and in the Time and Events Tables ([Table 1-1](#) and [Table 1-2](#)).

Table 5-1 Study Procedures

Visit Category	Procedures
Prevaccination Clinic Visit(s)	Section 5.1, Prevaccination Clinic Visits / Day 1 Prevaccination describes procedures to be followed prior to study vaccination: informed consent, screening, enrollment, and randomization
Vaccination Clinic Visit(s)	Section 5.2, Vaccination Clinic Visit(s) describes procedures to be followed during each clinic visit involving vaccination: vaccination, postvaccination procedures, and postvaccination reminders
Postvaccination Visit(s)	Section 5.3, Postvaccination Visits describes follow-up clinic visits and safety assessment calls
Unscheduled Visit(s)	Section 5.4, Unscheduled Visit(s) describes possible procedures to be followed at an unscheduled clinic visit
Study completion Visit	Section 5.5, Study Completion Visit describes procedures to be followed at the last study visit for a subject (may include early termination visit)

5.1 Prevaccination Clinic Visits / Day 1 Prevaccination

This section describes the procedures that must be performed for each potential subject prior to vaccination, including obtaining informed consent, screening, enrollment and randomization.

5.1.1 Informed Consent

"Informed consent" is the voluntary agreement of an individual or their parent(s)/LAR to participate in research. Consent must be given with free will of choice, and without undue inducement. The individual's parent(s)/LAR must have sufficient knowledge and understanding of the nature of the proposed research, the anticipated risks and potential benefits, and the requirements of the research to be able to make an informed decision.

Informed consent of the parent(s)/LAR following IRB guidance **must** be obtained before conducting any study-specific procedures (ie, all of the procedures described in the protocol). The process of obtaining informed consent should be documented in the subject source document in addition to maintaining a signed and dated version of the informed consent. Additional specifics regarding the informed consent processes are located in [Section 13.2, Informed Consent Procedures](#).

If the parent(s)/LAR are unable to read and write, a witness must be present during the informed consent discussion and at the time of informed consent signature. An “impartial witness” is defined as a person who is independent from study conduct, who cannot be unfairly influenced by those involved with the study, who attends the informed consent process if the subject or the subject's legally acceptable representative cannot read, and who reads the informed consent form (ICF) and any other written information supplied to the subject. After the written informed consent form and any other written information to be provided to subjects, is read and explained to the subject's parent(s)/LAR(s) and after the subject's parent(s)/LAR(s) has verbally consented to the subject's participation in the study and, if capable of doing so, has signed and personally dated the informed consent form, the witness should sign and personally date the consent form. By signing the consent form, the witness attests that the information in the consent form and any other written information was accurately explained to, and apparently understood by, the subject's parent(s)/LAR(s) and that informed consent was freely given by the subject's parent(s)/ LAR.

The informed consent process may be conducted within 10 days prior to Day 1.

5.1.2 Screening

After an individual's parent(s)/LAR has consented for the individual to participate in the study and informed consent is signed, sites will manually assign subjects a unique Screening Number. The subject's unique Screening Number will be documented in the Screening and Enrollment Log. The eligibility of the subject will be determined based on the inclusion and exclusion criteria listed in [Section 4, Selection of Study Population](#), and evaluated during this screening procedure.

Screening procedures will include the following:

1. Demographic data will be collected from the subject, including: date of birth, sex, race, ethnicity, height and weight.
2. The subject's prior influenza vaccination history will be obtained and recorded (“previously vaccinated” or “not previously vaccinated”). The Investigator will request a vaccination card or other documentation of previous vaccination history from the subject's parent(s)/LAR. If available, the card or other documentation will

be copied and placed in the subject's file to serve as source documentation. If documentation of vaccination history is not available, subject's parent(s)/LAR(s) verbal recall of prior vaccination will be recognized as sufficient medical history; this attempt and information must be captured in the source documentation. If the subject's parent(s)/LAR(s) is unable to recall previous vaccination status, then they should be considered "not previously vaccinated."

3. Relevant medical history will also be collected, including but not limited to any medical history that may be relevant to subject eligibility for study participation and previous and ongoing illnesses or injuries. Relevant medical history can also include any medical history that contributes to the understanding of an adverse event that occurs during study participation, if it represents an exacerbation of an underlying disease/pre-existing problem.
4. Perform a review of organ systems by interview that queries the subject or subject's parent(s)/LAR(s) as to any complaints the subject has experienced across each organ system. This will be performed before enrollment and used to guide physical examination. The general physical examination is to be performed by a qualified health care professional. Corresponding information is documented in the subject's source documents.
5. If applicable, prior and concomitant medications or vaccinations taken up to 1 month prior to start of study should be collected (refer to [Section 6.5, Prior and Concomitant Medications and Vaccines](#) for further details).
6. Collection of clinical signs is to be performed: weight, height and body temperature. If body temperature is $\geq 38.0^{\circ}\text{C} / \geq 100.4^{\circ}\text{F}$ at the time of screening, vaccination must be postponed until 3 days after the fever has resolved (see [Section 4.3, Criteria for Delay of Vaccination](#)).
7. The use of antipyretics and/or analgesic medications within 24 hours prior to vaccination must be identified and the reason for their use (prophylaxis versus treatment) must be described in the source document and Concomitant Medications CRF. The use of antipyretics/analgesics within 24 hours prior to vaccine administration is a reason to delay study vaccination (see [Section 4.3 Criteria for Delay of Vaccination](#), and [Section 6.5, Prior and Concomitant Medications and Vaccines](#)).
8. Prior to vaccination, blood will be drawn from all subjects ([Section 5.1.5, Blood Draw](#)).

Measurement and recording of clinical signs, height, weight, and body temperature may be conducted by a trained health care professional (see [List of Definitions](#)).

A general physical examination is to be performed by a qualified health care professional (see [List of Definitions](#)).

The data described above will be written in the source document and entered in eCRF (see [Section 9.1, Source Documentation](#)). Should the physical assessment reveal any abnormal values or events, these must be documented as part of medical history.

In the event that the individual is determined ineligible for study participation, he/she is considered a screen failure. The reason for screen failure must be documented in the Screening and Enrollment Log. If the individual is determined to be eligible for the study, he/she will be enrolled into the study.

5.1.3 Enrollment

After signing the informed consent form and review of eligibility criteria, if an individual is determined to be eligible for study participation, the investigator or delegate will enroll the subject and enter subject information and stratification information into the Interactive Response Technology (IRT) system.

5.1.4 Randomization

Enrolled subjects will be randomized in the IRT system by a 2:1 ratio and automatically assigned a unique Subject ID. Subjects participating in the CMI group (approximately 84 subjects) will be enrolled in a limited number of sites through sequential allocation (in principle, subjects in which CMI will be evaluated will be enrolled first). The Subject ID will be the subject's unique identification (ID) number for all eCRFs and associated study documentation that will be used for duration of the study. After randomization, the Screening Number ceases to be used and remains in the Screening and Enrollment Log only. The list of randomization assignments is produced by the EDC/IRT service provider.

Stratification through IRT will be used to ensure a balanced distribution among the age groups, at least 30% of subjects should be 6 through 23 months and at least 30% of subjects should be from 24 through 47 months of age.

For A/H1N1, B/Victoria, and B/Yamagata strains, immunogenicity of QIVc and US-licensed QIV will be evaluated by MN assay in a 20% subset of subjects. After blood specimens have been collected a randomly selected subset (20%) of these samples will be analyzed. Detailed information regarding the randomization procedures associated with the selection of the samples to be analyzed can be found in the Statistical Analysis Plan (SAP).

If for any reason, after signing the Informed Consent Form (ICF), the subject who is eligible and enrolled fails to be randomized, this is called a randomization failure. The reason for all randomization failures should be recorded in the Screening and Enrollment Log and in the source document as specified in the Source Document Agreement (SDA). The information on subjects who are randomization failures should be kept distinct from subjects who are screen failures, as described in [Section 5.1.2, Screening](#).

If for any reason, after randomization the subject fails to undergo treatment, this is an Early Termination and the reason should be recorded in source document as specified in the SDA. The information on these Early Termination subjects should be kept distinct in the source documentation from randomization failures.

5.1.5 Blood draw

After randomization, but prior to vaccination, all subjects will have approximately 8 mL of blood drawn for immunogenicity evaluation or to assess CMI response. Since there are 2 blood draws per subject, the total blood volume drawn per subject in this study is approximately 16 mL. Details regarding the volume of blood and testing to be performed are in Section 3.5. (see [Section 3.5, Collection of Clinical Specimens](#)). These data will be written in the source document (see [Section 9.1, Source Documentation](#)) and must be documented in the eCRF.

5.2 Vaccination Clinic Visit(s)

Please refer to the Time and Events Tables ([Table 1-1](#) and [Table 1-2](#)). Vaccination will be performed on Day 1 (all subjects) and Day 29 (“not previously vaccinated” subjects) using the vaccine identified by the assigned Pack ID.

After completing the prevaccination procedures as described in [Section 5.1, Vaccination Clinic Visit – Day 1 Prevaccination Procedures](#), the vaccine will be administered to the subject according to the procedures described in [Section 6.3, Vaccine Preparation and Administration](#), observing the blinding procedures described in [Section 3.3, Blinding Procedures](#).

Prior to administration of the study vaccination, it needs to be confirmed that the subject is eligible for vaccination and does not meet any criteria for exclusion or delaying study vaccination as described in [Section 4, Selection of Study Population](#).

5.2.1 Day 1 Postvaccination Procedures (All Subjects)

The following postvaccination procedures will be performed:

1. Training should be directed at the individual(s) who will perform the measurements of local reactions and body temperature, and those who will enter the information into the subject diary card. This individual may not be the subject's parent(s)/LAR(s), but if a person other than the subject's parent(s)/LAR(s) enters information into the subject diary card, this person's identity must be documented in the study file and this person must receive training on the diary card. Training of the subject's parent(s)/LAR(s) on how to measure an injection site reaction should be performed while the subject is under observation after vaccination.

Subject Diary Card instruction must include the following:

1. The subject's parent(s)/LAR(s) must understand that timely completion of the Subject Diary Card on a daily basis is a critical component to study participation. The subject's parent(s)/LAR(s) should also be instructed to write clearly and to complete the Subject Diary Card in pen. Any corrections to the Subject Diary Card that are performed by the person completing the Subject Diary Card should include a single strikethrough line with a brief explanation for any change. **No changes can be made to the Subject Diary Card after it is returned to the clinic.**
2. Starting on the day of vaccination, the subject's parent(s)/LAR(s) will check in the evening for specific types of reactions at the injection site (solicited local adverse reactions), any specific generalized symptoms (solicited systemic adverse events), body temperature any other symptoms or change in the subject's health status, and any medications/vaccinations taken (excluding vitamins and minerals). These solicited adverse events and body temperature will be recorded in the "six hours" location on the Subject Diary Card.
3. Body temperature measurement is to be performed using the thermometer provided by the site. In children younger than 36 months of age, measurement of temperature rectally is preferred. Oral, axillary or tympanic membrane routes may be used in older children. If the subject appears unusually hot or cold during the day, the subject's parent(s)/LAR(s) should check body temperature. If the subject has fever, the highest body temperature observed that day should be recorded on the Subject Diary Card. The measurement of solicited local adverse reactions is to be performed using the ruler provided by the site.
4. The collection of body temperature, solicited local adverse reactions, solicited systemic adverse events on the Subject Diary Card will continue for a total of 7 days.
2. After vaccination, the subject will be observed for at least 30 minutes including observation for local and systemic adverse events, unsolicited AEs, and body temperature measurement. Please take the opportunity to remind the subject's parent(s)/LAR(s) how to measure solicited adverse events and body temperature as part of this observation

period. Record all safety data collected in the source documents. **The 30-minute observation data must be recorded in the source documents only; not in the Subject Diary Card.**

3. Schedule the next study activities, reminder telephone call, and clinic visit, with the subject's parent(s)/LAR(s).
4. Remind the subject's parent(s)/LAR(s) to complete the Subject Diary Card daily and to contact the site if there are any questions and to contact the site immediately (or as soon as the subject is medically stable) if the subject has a medical condition that leads to a hospitalization.

5.2.2 Day 29 Prevaccination Procedures (“not previously vaccinated” subjects)

The following procedures should be carried out at the clinic visit on Day 29 before the vaccination is performed:

1. At the clinic visit, the Subject Diary Card will be reviewed. Please see [Section 3.4.2, Tools Used for Data Collection](#) for additional guidance on Subject Diary Card review.

The qualified health care professional will interview the subject's parent(s)/LAR(s) to obtain information relating to unsolicited AEs including SAEs, AEs leading to study or vaccine withdrawal, NOCDs, associated concomitant medications and all vaccinations (see [Section 6.5, Prior and Concomitant Medications and Vaccines](#)). All safety information described by the subject's parent(s)/LAR(s) must be written down in the source documents.

2. Perform a review of organ systems by interview that queries the subject's parent(s)/LAR(s) as to any complaints the subject has experienced across each organ system. This will be used to guide the physical examination. Corresponding information is documented the subject's source documents.
3. Take body temperature. In children younger than 36 months of age, measurement of temperature rectally is preferred. Oral, axillary or tympanic membrane routes may be used in older children. If the body temperature is $\geq 38.0^{\circ}\text{C} / \geq 100.4^{\circ}\text{F}$, vaccination must be postponed until 3 days after the fever has resolved. Vaccination is also postponed for any clinically significant active infection based on investigator's clinical judgment (see [Section 4.3, Criteria for Delay of Vaccination](#)).
4. The use of any analgesics (oral, topical, etc.) and/or antipyretics within 24 hours prior to vaccination is a reason to delay vaccination (see [Section 6.5, Prior and Concomitant Medications and Vaccines](#)). Use of these medications can decrease the immune response to the vaccination. Verify that the subject has not applied topical analgesic/anesthetic to the anticipated injection site within the past 24 hours, as application of

analgesic/anesthetic patch/cream may interfere with the ability to interpret local reactions after vaccination. If topical analgesic/anesthetic has been applied to the area to be injected, the opposite limb that has not been treated with analgesic/anesthetic may be injected. If subject took oral antipyretics and/or analgesic medications within 24 hours prior to vaccination, document this and the reason for their use (prophylaxis versus treatment) in the subject's source record and eCRF.

Prior to receipt of second study vaccination ("not previously vaccinated" children), subjects must be evaluated to confirm that they are eligible for subsequent vaccination. If subjects meet any of the original exclusion criteria (except for those listed under [Section 4.2, Exclusion Criteria](#)) or meet any of the criteria listed under [Section 4.3, Criteria for Delay of Vaccination](#), they should not receive additional vaccinations. This reassessment of eligibility should be documented in source documents; if the subjects is found not eligible for the second vaccination, the reason for not administering scheduled vaccine should be documented in eCRF.

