^a Confirm consent form(s) signed prior to any procedures. The informed consent process may be conducted earlier, but within 10 days prior to Day 1.

^b Procedures to be performed prior to vaccination.

^c Includes measurement of height and weight..

^d A blood sample will be drawn prevaccination (Day 1) and postvaccination (Day 29) for immunogenicity evaluation or for assessing cell-mediated immunity response.

Table 1-2 Time and Events Table – Not Previously Vaccinated Subjects

Visit Number	Treatment Period					Follow-up Period	
	Clinic Visit	Reminder Phone Call	Clinic Visit	Reminder Phone Call	Clinic Visit	Safety Phone Call	Safety Phone Call
V1			V2		V3	V4	V5
Study Day		V1 + 2	V1 + 28	V2 + 2	V2 + 28	V2 + 90	V2 + 180
Study Day Window	n/a	-1/+1	0 to +7	-1/+1	0 to +7	0 to +7	0 to +14
Informed Consent ^a	X ^b						
Medical History	X ^b						
Physical Examination and Clinical signs	X ^{b, c}		X		X		
Exclusion/Inclusion Criteria	X ^b		X ^{b, d}				
Randomization	X ^b						
Vaccination	X		X				
30 Minutes Post Vaccination Assessment	X		X				
Subject Diary Card Dispensed with Training	X		X				
Subject Diary Card Reminder Call		X		X			
Subject Diary Card Reviewed and Collected			X		X		
Assess all AEs	X		X		X		
Assess SAEs, NOCDs, AEs leading to withdrawal	X		X		X	X	X
Assess Relevant Medications/Vaccinations	X		X		X	X	X
Blood Draw	X ^{b, e}				X ^e		

Abbreviations: AE = adverse event; n/a = not applicable; NOCD = new onset of chronic disease; SAE = serious adverse event; V = visit.

^a Confirm consent form(s) signed prior to any procedures. The informed consent process may be conducted earlier, but within 10 days prior to Day 1.

^b Procedures to be performed prior to vaccination.

^c Includes measurement of height and weight.

^d Eligibility for subsequent vaccination (see 5.2.2).

^e A blood sample will be drawn prevaccination (Day 1) and postvaccination (Day 57) for immunogenicity evaluation or for assessing cell-mediated immunity response.

LIST OF ABBREVIATIONS

AE	Adverse Event
BLA	Biologics License Application
CBER	Center for Biologics Evaluation and Research
CHMP	Committee for Medicinal Products for Human Use
CI	Confidence Interval
CMI	Cell Mediated Immunity
CRF	Case Report Form
CRO	Contract Research Organization
CSR	Clinical Study Report
DMC	Data Monitoring Committee
eCRF	Electronic Case Report Form
EDC	Electronic Data Capture
EMA	European Medicines Agency
ESP	External Service Provider
FAS	Full Analysis Set
FDA	Food and Drug Administration

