5.2.3 Day 29 Postvaccination Procedures ("not previously vaccinated" subjects)

After confirming subject continues to meet study eligibility criteria by completing procedures outlined in [Section 5.2.2, Day 29 Prevaccination Procedures \(not previously vaccinated subjects\)](#) above, perform vaccination of the subject according to the assigned study vaccine and according to the procedures described in [Section 6, Treatment of Subjects](#).

The following postvaccination procedures should be carried out on Day 29:

1. Careful re-training, if necessary, of the subject's parent(s)/LAR(s) on how to measure local reactions and body temperature, how to complete and how often to complete the Subject Diary Card is crucial. Reference [Section 5.2.1, Day 1 Postvaccination Procedures \(All Subjects\)](#) for Subject Diary Card instruction. Any re-training must be recorded in the source documents.
2. After vaccination, the subject will be observed for at least 30 minutes including observation for local and systemic adverse events, AEs, and body temperature measurement. Please take the opportunity to remind the subject's parent(s)/LAR(s) how to measure solicited adverse events and body temperature as part of this observation period. Record all safety data collected in the source documents. **The 30-minute observation data must be recorded in the source documents only; not in the Subject Diary Card.**
3. Schedule/review the next study activities, reminder telephone calls, and clinic visit, with the subject's parent(s)/LAR.

Remind the subject's parent(s)/LAR(s) to complete the Subject Diary Card daily and to contact the site if there are any questions and to contact the site immediately (or as soon as the subject is medically stable) if the subject has a medical condition that leads to a hospitalization.

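### The second-dose eligibility sentence in Protocol 5.2.2 exempts the protocol's only exclusion list and is ambiguous about delay criteria; a minor wording error worth correcting

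*Protocol*

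**What the plan says.** Children classed as not previously vaccinated receive a second dose at Visit 2 (Day 29). Under Protocol 3.1 this class includes every eligible child under 12 months.

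The last paragraph of Protocol 5.2.2 tells the site how to decide on that dose. It opens "If subjects meet any of the original exclusion criteria (except for those listed under" Section 4.2, Exclusion Criteria. It continues "or meet any of the criteria listed under" Section 4.3, Criteria for Delay of Vaccination. Children caught by either limb should not be vaccinated further, and the site records in the eCRF why the scheduled dose was not given.

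Other parts of the protocol cover the same decision:

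- **Section 4.2, closing paragraph**, withholds dose 2 "If subjects meet any of the original exclusion criteria listed above or experienced severe tolerability issues after first study vaccination".
- **Section 5.2**, which covers Day 1 and Day 29, sets this condition on giving a dose: "it needs to be confirmed that the subject is eligible for vaccination and does not meet any criteria for exclusion or delaying study vaccination".
- **Section 5.2.2, step 3**, says of a raised temperature that "vaccination must be postponed until 3 days after the fever has resolved". **Step 4** says that analgesic or antipyretic use "within 24 hours prior to vaccination is a reason to delay vaccination".
- **Section 4.3** describes these circumstances as transient, allows eligibility after the window has passed and criteria are rechecked, and does not count the missed visit window as a deviation.
- **Section 6.3** refers the first dose to Sections 4.1 and 4.2, but subsequent doses to Section 4.3 only.
- **Table 1-2, footnote d**, attached to the Visit 2 eligibility entry, reads "Eligibility for subsequent vaccination (see 5.2.2".

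**The concern.** The sentence is an operative dosing rule that sites are sent to. Footnote d of Table 1-2 names Section 5.2.2, and Section 5.2.3 allows dose 2 "After confirming subject continues to meet study eligibility criteria by completing procedures outlined in" that same section. Taken literally, the rule has two faults.

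First, it tells the site to check the exclusion criteria and then exempts all of them. Suppose an immunodeficiency is first suspected between Day 1 and Day 29 (exclusion criterion 5a). Sections 4.2 and 5.2 bar dose 2, while the sentence in 5.2.2 exempts the criterion.

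Second, it attaches a no-further-vaccination outcome to conditions that the protocol elsewhere treats as short delays. For a child with fever at Day 29, step 3 postpones the dose, while the closing sentence can be read as withholding it. That child would then receive one of two planned doses.

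At stake are a clear safety check in young children and consistent completion of the two-dose schedule. Section 3.8 also tells investigators not to seek approval for deviations, so a site cannot settle the conflict that way.

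**Working it through.** The plan gives no figure on this point and no arithmetic is needed beyond a count. The check is a comparison of texts.

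**Step 1. What does the exception remove?** Section 4.2 lists criteria 1 to 11, and the protocol has no other exclusion list. The exception therefore covers 11 of 11. The cross-reference carries the title of Section 4.2 as well as its number, so this is neither a lost digit nor a redaction.

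**Step 2. Does the rule agree with the others?**

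| Place | Child meets a Section 4.2 criterion at Day 29 | Child meets a Section 4.3 criterion at Day 29 |
|---|---|---|
| 5.2.2, closing paragraph | Exempted | No further vaccination; no time limit stated |
| 5.2.2, steps 3 and 4 | Not addressed | Postpone or delay |
| 4.2, closing paragraph | No dose 2 | Not addressed, apart from criterion 1 (step 5 below) |
| 4.3 | Recheck criteria after the delay | Transient; eligible after the window |
| 5.2 | Must not be met before vaccination | Must not be met before vaccination |
| 6.3, subsequent doses | Not mentioned in the eligibility sentence | Follow Section 4.3 |

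In the first column, 5.2.2 contradicts Sections 4.2 and 5.2, and the eligibility sentence in 6.3 does not settle the matter. In the second column, 5.2.2 is at odds with its own steps 3 and 4 and with Section 4.3.

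**Step 3. How firm is the second inconsistency?** Two readings are open. The first is that the child is not vaccinated at this visit. It fits the title of Section 4.3 and the mandatory postponement a few lines earlier. The second is that dose 2 is lost. It fits the absence of any time limit, and the next sentence, which speaks of a child found not eligible for the second vaccination. The text does not choose between them, so this half is an ambiguity rather than a clear permanent bar.

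**Step 4. What else would stop a wrong dose?**

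- Section 4.1 re-evaluates inclusion criteria 3 and 4, including general good health in the investigator's judgement, before dose 2.
- The closing paragraph of Section 4.2 sits inside the section that the faulty cross-reference points to.
- Section 5.2 requires the full check before study vaccination.
- Section 6.5 has concomitant medications and vaccines checked against Section 4; step 1 of 5.2.2 leads there.
- Table 1-2 marks the exclusion/inclusion row at Visit 2, although footnote d on that cell points back to 5.2.2.
- Section 6.3 requires that vaccination be clinically appropriate in the investigator's judgement.

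In the immunodeficiency example, Sections 4.1 and 6.3 could each stop the dose even if 4.2 and 5.2 were overlooked.

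**Step 5. Would a simple rewrite work?** Not quite. Exclusion criterion 1 is acute (severe) febrile illness, and it refers to Section 4.3. A sentence saying that any Section 4.2 criterion bars dose 2 and any Section 4.3 criterion postpones it would put a severely febrile child under both clauses. The closing paragraph of Section 4.2 already has this problem. The correction needs an exception for criterion 1 in both places.

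**The case against.** The strongest reply is that no site would act on the parenthesis. It cancels its own clause, so a reader would recognise a slip, follow the link to Section 4.2 and find the correct rule there. The Visit 2 entry in Table 1-2 orders the check, and SAP Appendix A calls the schedule binding where the protocol is inconsistent. Section 5.2.3 asks the site to confirm continued eligibility. The count of 11 is also a count of list items, not of effect: criteria 6 and 10, items 5b and 5c and the first part of 7 are tied to the time before consent, so they cannot newly arise by Day 29 and could only be discovered late.

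Most of this stands and is why the point is minor. It does not make the sentence right. The schedule's own footnote sends the reader to 5.2.2, and the subsequent-dose sentence in 6.3 leaves out Section 4.2.

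A reader might infer more: that the protocol in effect allows excluded children to be dosed, or that any child febrile at Day 29 permanently loses dose 2. The documents do not support either. The first overlooks the safeguards in Sections 4.1, 4.2, 5.2, 6.3 and 6.5 and in Table 1-2. The second requires setting aside the mandatory postponement in step 3 of the same section.

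**Conclusion.** The sentence in Protocol 5.2.2 is wrong as written on the exclusion check and ambiguous on the delay criteria. It is a minor wording error that could usefully be corrected. The first part rests only on Section 4.2 being the sole exclusion list, which the protocol confirms. The second part is an internal inconsistency with a plausible benign reading.

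The rule applies at Visit 2 to every not previously vaccinated child. The documents give no rate of exclusion or delay criteria at Day 29, so the number of children affected cannot be estimated. No effect on power, sample size or analysis sets is claimed, and none should be inferred. What the parenthesis was meant to exempt cannot be determined from the documents.

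**What to change.** Replace the sentence in Protocol 5.2.2 with:

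> Subjects who meet any exclusion criterion in Section 4.2 other than criterion 1, or any other bar to the second dose in Sections 3.8, 4.1 or 4.2, should not receive the second vaccination. For subjects who meet exclusion criterion 1 (acute severe febrile illness) or any criterion in Section 4.3, the second vaccination is postponed until the condition has resolved, the delay window has passed and eligibility has been rechecked.

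The other bars it refers to are a related SAE (Section 3.8), failure of inclusion criteria 3 or 4 (Section 4.1) and severe tolerability issues after dose 1 (Section 4.2).

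Two matching edits are needed. Add the same exception for criterion 1 to the dose-2 paragraph that closes Section 4.2. In Section 6.3, refer subsequent doses to Sections 4.1, 4.2 and 4.3. Footnote d of Table 1-2 can stay, since it would then point to a correct rule.

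The cost is wording in three places. Section 13.4 treats a formal clarification that may affect conduct or subject safety as an amendment, so it needs IRB approval, and sites must be notified. No visits, procedures or subjects are added.
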